Hypothesis 1.6 (secondary): Those assigned to placebo will have a higher rate of cotinine-verified, seven-day point-prevalence nicotine vaping abstinence at end of treatment compared to EUC.

Hypothesis 1.7 (exploratory): Those assigned to varenicline will have an earlier onset of abstinence, longer latency to first lapse, longer latency to relapse, longer duration of abstinence, and greater total number of days of vaping abstinence than those assigned to placebo or EUC as

determined by using data ascertained daily with the emocha Mobile Health app (emocha) or REDCap surveys.

Aim 2 (secondary): To establish the safety and tolerability of varenicline in adolescents attempting to quit vaping nicotine.

Hypothesis 2.1: Nicotine withdrawal symptoms, craving, and negative mood symptoms will be less frequent and severe in the varenicline group than the placebo or EUCgroups.

Hypothesis 2.2: Those assigned to varenicline will have no greater incidence or severity of adverse events (AE) compared with those assigned to placebo or EUC during treatment and follow-up.

Aim 3 (exploratory): To assess if there are between group differences in consumption of alcohol, combusted tobacco, cannabis, and non-medical prescription drugs during the treatment and follow-up periods.

Exploratory Hypothesis: Those assigned to varenicline will have less consumption of alcohol, combusted tobacco, cannabis, and non-medical prescription drugs and greater reduction in severity of nicotine dependence as assessed with the ECDI during the treatment and follow-up periods than those in the placebo or EUC groups.

PILOT STUDY 2020P002774-Pilot - NCT04602494

In 2021, during the national recall of varenicline in the US, the FDA provided temporary authorization for importation of apo-varenicline from the Canadian company, Apotex. A pilot vaping cessation trial was conducted using apo-varenicline or identical placebo in 4 study participants who met inclusion and exclusion criteria below except that the age range was limited to 18-25. In this pilot trial, all study procedures listed below were piloted, including the emocha platform for study medication adherence and daily report of vaping behavior and adverse effects and the novel, brief lay-counselor behavioral vaping cessation intervention.

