Eligible participants will be randomly assigned in a 1:1:1 ratio, in blocks of 6, to varenicline, identical appearing placebo prepared by the MGH research pharmacy, or EUC (i.e., TIQ and monitoring with assessments only). Study staff and participants will both be blind to drug for those randomized to the varenicline and placebo arms. Randomization will be stratified by secondary or post-secondary school status. The randomization scheme will be computer generated by the MGH Research Pharmacy by personnel with no other interactions with study staff or participants. There will be separate randomization codes for apo-varenicline, imported from Canada under a provisional FDA allowance, and domestic generic varenicline with full FDA approval. The randomization codes will be held in the MGH research pharmacy, and available to study PIs only in the case of urgent medical need. Assessments will be conducted by study staff who are blind to study intervention. Treatment will be assigned according to study

number, assigned sequentially to eligible participants who enroll in the trial and attend the baseline visit.

Special considerations for individuals living in the same households: More than one household member or family member will be allowed to participate in the study. Since there is a possibility that participants from the same household, voluntarily or not, share study medication, participants from the same household will be yoke randomized, eg assigned to the same intervention. Yoked randomization will ensure members of the same household or family members receive the same intervention and will reduce the risk for contamination.

V. STUDY PROCEDURES

Participants will be randomly assigned to receive a 12-week course of varenicline, an identical placebo, or EUC only. Participants assigned to receive varenicline or identical placebo will receive individual behavioral vaping cessation sessions (held virtually by videoconferencing or in-person), and a digital platform to report vaping behavior, study medication adherence, and tolerability. Participants in EUC will be provided with explicit advice to quit and non-directive support. Participants in all three arms will complete assessments, conducted by raters blinded to study arm assignment, and will include samples for cotinine assays and self-reports of vaping and other drug use. Participants in all three arms will receive an introduction to TIQ and receive weekly monitoring of TIQ use from study staff.

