a. Study visits and parameters to be measured

The enrollment visit will be conducted in person and will include a detailed description of the study, informed consent/assent, assessments to confirm eligibility, assessments of vaping and other drug use behavior, and medical and psychiatric diagnostic and symptom assessments. Eligible, consented participants will then be scheduled for a baseline assessment visit where they will receive study medications (for those randomized to varenicline or placebo arms), weekly visits which will include assessments (all participants) as well as the behavioral vaping cessation sessions (for those randomized to varenicline or placebo arms), and monthly assessment visits. Following completion of the 12-week intervention period, participants will be scheduled for follow-up visits at weeks 16, 20, and 24. Study visits will be conducted at our MGB location, or in a private room at a participant's local library or current school. When conducting a study visit at a site external to MGH, study staff will obtain verbal permission from library/school administrators to conduct study visits at a given location. When obtaining permission to conduct a visit, no identifying or specific information regarding the participant or the study will be mentioned. All study visits can be conducted in person or virtually. We have piloted procedures and have a standard operating procedure for sending materials to conduct urine drug and pregnancy screening during virtual visits. Study staff will include instructions for participants to perform the tests and hold the assays up to their device's camera so study staff can record urine screening results. Height and weight will be recorded per participant's report for remote visits. Carbon monoxide will not be recorded for virtual visits, and we will rely on participant reported combusted tobacco use. Medication will be shipped via priority mail if a visit where medication is distributed is done virtually. Blood pressure and heart rate will not be collected if a visit is virtual, as these are not necessary measures in prescribing varenicline or part of our primary outcomes.

Time and Events Table

Time and Events

| | | | Follow-up period | | | | | | | | |
|--|------------|-------------|------------------|---------|-----------|---------|------------|----------|----------|----------|----------|

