| Assessments | Enrollment | BL (Wk0) | Wk 1-3 | Wk 4 | Wk 5-7 | Wk 8 | Wk 9-11 | Wk 12 | Wk 16 | Wk 20 | Wk 24 |
| Screening | |   | - | | - | - | - | | - | - | |
| Consent | Х | - | - | - | - | - | - | - | - | - | - |
| Demographics, Vaping history | Х | - | - | - | - | - | - | - | - | - | - |
| Primary outcomes | | | | | | | | | | | |
| Salivary cotinine*** | Х | Х | Х | Х | Х | Х | х | Х | Х | Х | Х |
| Timeline followback (TLFB) | х | Х | Х* | Х | Х* | Х | Х* | х | х | Х | Х |
| Daily vaping exposure y/n via REDCap (for those not randomized to EUC) | - | Х | Х | х | х | х | Х | Х | - | - | - |
| Secondary/exploratory outcomes | ; | | | | | | | | | | |
| MNWS | Х | Х | Х | Х | Х | Х | Х | Х | - | - | - |
| QVC | Х | х | х | Х | Х | Х | х | х | - | - | - |
| MASQ-D30 | х | Х | - | Х | - | Х | - | х | х | Х | Х |
| NAEI | х | х | - | х | - | х | - | х | х | Х | Х |
| Adverse events | - | х | Х | Х | Х | Х | х | х | х | Х | Х |
| Other biomarkers | | | | | | | | | | | |
| Urine NNAL | - | х | - | - | - | - | - | х | - | - | Х |
| ТНС-СООН | - | х | - | - | - | - | - | х | - | - | Х |
| СО | х | - | - | - | - | - | - | - | - | - | - |
| Pregnancy test | х | х | - | х | - | х | - | х | - | - | - |
| Drug screen | х | х | - | х | - | х | - | х | х | х | х |
| Vital signs | х | х | - | х | - | х | - | х | - | - | - |
| Height and weight | х | - | - | - | - | - | - | - | - | - | - |
| Saliva (genetics) | х | - | - | - | - | - | - | - | - | - | - |
| Descriptions, effect modifiers, cov | variates | | | | | | | | | | |
| Medical History | х | - | - | - | - | - | - | - | - | - | - |
| Concomitant medications | х | х | х | х | х | х | х | х | х | х | Х |
| ECDI | х | - | - | - | - | - | - | х | - | - | Х |
| AUDIT | х | - | - | - | - | - | - | х | - | - | Х |
| CUDIT | х | - | - | - | - | - | - | х | - | - | Х |
| BRIEF-SR | х | - | - | - | - | - | - | х | - | - | - |
| C-SSRS | Х | - | - | - | - | - | - | - | - | - | - |
| WTAR | Х | - | - | - | - | - | - | - | - | - | - |
| UPPS-P | Х | - | - | - | - | - | - | - | - | - | - |
| CHRT | - | Х | - | Х | - | Х | - | Х | -X | -X | -X |
| Flavor preferences | х | - | - | - | - | - | - | - | - | - | - |
| Peer and family influence on vaping | х | - | - | - | - | - | - | - | - | - | - |
| PATH Instruments: Vaping and substance use history, modified WTQ, MTQ | Х | - | - | - | - | - | - | - | - | - | - |
| YSS | - | - | - | - | - | - | - | Х | - | - | - |

| TIQ | - | х | Х | Х | Х | х | х | х | - | - | - |

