Before behavioral intervention sessions, participants will fill out assessments of vaping craving and collect saliva for cotinine testing (the latter only occurring if the participant self-reports nicotine abstinence since the last weekly visit). To refine and tailor these interventions to be maximally appealing to and effective for adolescents who vape, we will ask participants for weekly feedback on the appeal, relevance, and effectiveness of the educational topics and skills covered in the program. For participants randomized to the EUC arm, weekly sessions will only consist of non-directive support and assessments noted in the Time and Events Table, including saliva samples for cotinine (collected only to bio-verify self-reported nicotine abstinence).

| Time | Activities |
|--------|---|
| 5 mins | Check-in on adverse events, vaping exposure, and medication adherence |
| 3 mins | New educational content |
| 7 mins | Review of education material and skill/behavior goal |

CBT Structure

Prior to initiating the study intervention, interventionists will complete training conducted by [name] or other doctoral members of study staff on QuitVaping sessions. This will include didactic training on vaping and vaping cessation in adolescents, study methods, theoretical rationale, and background information on the behavioral and pharmacologic interventions. At the end of the training, leaders must achieve a minimum score of 80% on the fidelity scale based on their facilitation of two simulated sessions before they lead a session.

e. Enhanced Usual Care (EUC)

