The Behavior Rating Inventory of Executive Function—**Self-Report (BRIEF-SR)**⁷² is a standardized 80-item self-report behavior rating scale that assesses impulsivity in cognition, behavior, and executive functioning skills. The BRIEF-SR will be administered at enrollment and week 12.

emocha Mobile Health is a mobile health platform that uses video technology and human engagement to monitor patient behavior and enable remote engagement in clinical trials. The emocha platform is globally compliant in terms of data protection standards, including GDPR ready, EU-US Privacy Shield certified, and HIPAA compliant. For those randomized to varenicline or placebo, emocha will be used to send twice daily reminders to take study medication and remotely monitor study medication dosing. Participants will record daily vaping either via emocha or REDCap.

Measures of Vaping abstinence: Saliva will be collected weekly during the treatment phase and then monthly for semi-quantitative cotinine measurement to verify nicotine abstinence in participants who self-report abstinence. Only at enrollment and baseline will cotinine be collected despite self-report to verify use. For in-person sessions, saliva will be collected before the session. For remote sessions, a handout with instructions, materials, and barcoded kits unique to participant will be mailed to participants to perform weekly before their weekly assessment visits. We developed SOPs for safe at home collection and mailing of biological specimens, a procedure we piloted during the closure of MGH clinical research facilities from March-June 2020. Semi-quantitative cotinine of <30ng/ml will validate self-reported nicotine vaping abstinence since the last visit. Those who report no vaping use since the last study visit but who have a cotinine >30ng/ml will be considered non-abstinent at that visit for the analyses.

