Measures of smoking abstinence: Carbon monoxide (CO) in expired air will be measured at enrollment with a small, hand-held CO monitor. To do so, participants will blow into a straw attached to the device, a Bedfont Smokerlyzer II (Kent, England), following a 15-second breathhold to verify self-report of non-smoking status. Expired CO <5 parts per million (ppm) is consistent with smoking abstinence. Assays for NNAL will be conducted on urine collected at baseline and weeks 12 and 24. NNAL <10pg/ml will be considered a more sensitive verification of self-report of no combusted tobacco use in the past 2-3 months. Participants with an NNAL of <10pg/ml at baseline and >10pg/ml during the study will be considered to have initiated combusted tobacco use during the trial.

Timeline Follow-Back (TLFB): The TLFB will assess tobacco vaping, smoking, cannabis, and alcohol use. It will be administered at enrollment, baseline, monthly, and follow-up visits. A modified TLFB of vaping in the past 7 days will be administered at weekly intervention visits.

**Pregnancy test:** Urine will be collected from biological females at enrollment, baseline, week 4, week 8, and week 12 for a pregnancy test.

Drug testing: Urine will be collected at enrollment, baseline, and monthly assessments to screen for recent use of cannabis, amphetamines, methamphetamine, cocaine, opiates, barbiturates, benzodiazepines, phencyclidine, methadone, and oxycodone. Quantitative assessment of THC metabolites in urine will be conducted at baseline, week 12, and week 24 to assess for new cannabis use or change in cannabis use during the trial.

Perceived treatment assignment: To assess participants' guess of their treatment assignment, participants will be asked, "what treatment do you think you received? This will be followed by one open-ended question: "Why do you think you received that treatment?" No clarifications will be asked, nor will participants be probed to expand on their answers. This question will be asked either at the end of the week 12 visit or their termination visit.

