Participants will be compensated \$30 for the enrollment visit and all subsequent weekly and follow-up visits. Participants will be paid \$50 (varenicline and placebo) or \$100 (Enhanced Usual Care) for completion of monthly visits during the treatment period. Participants will be paid up to \$2 per day (up to \$168 total) for emocha medication adherence and REDCap survey completions (for those not randomized to EUC). All participants who complete the study will be automatically entered into a raffle for a study completion bonus. For a more detailed description of our payment schedule, refer to the table below. Participants will be reimbursed up to \$15 for necessary travel related to in-person visits. Participants will be compensated for study visits either via MGB-issued check or using the MGB Advarra Participant Payment system, a cloudbased application that provides subjects with a reloadable Visa card that is credited with fixed stipends following specified data collection points. Participants will be informed of Advarra policy during the consent process. After agreeing to participate in the study, participants will also be asked to sign a "Advarra Participant Payment Card Acknowledgement of Receipt" form to certify their understanding of Advarra Participant Payment policies. The form will require participants to print and sign their name and provide their social security number. If the participant is under 18 years old, then parent/guardian information including date of birth, social security number, and address will be collected. Advarra acknowledgment forms will be stored in a locked study cabinet. Travel reimbursement as well as emocha/REDCap adherence will issued to participants as a lump sum via check at the conclusion of their study participation. Participants will be paid using gift cards if they cannot be paid via Advarra/check using a social security number/individual taxpayer identification number.

| Visit/Week | Varenicline/Placebo | EUC | | |
|------------------|---------------------|------|--|--|
| Enrollment | 30 | 30 | | |
| Weeks 0, 1, 2, 3 | 30 | 30 | | |
| Week 4 | 50 | 100 | | |
| Weeks 5, 6, 7 | 30 | 30 | | |
| Week 8 | 50 | 100 | | |
| Weeks 9, 10, 11 | 30 | 30 | | |
| Week 12 | 50 | 100 | | |
| Week 16, 20, 24 | 30 | 30 | | |
| Emocha + surveys | 168 | 0 | | |
| Total | 738 | 720 | | |
| Raffle Bonus | 450 | 468 | | |
| Grand Total | 1188 | 1188 | | |

Payment Schedule

VI. BIOSTATISTICAL ANALYSIS

Statistical Design and Power:

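### Exploratory Hypothesis 1.7 compares varenicline with enhanced usual care on daily vaping reports that the plan does not collect in enhanced usual care; the Timeline Followback should be the named source for those contrasts.

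*Combined protocol and SAP*

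**What the plan says.** Section II, Hypothesis 1.7, predicts that varenicline will do better than placebo or EUC on five endpoints: onset of abstinence, time to first lapse, time to relapse, duration of abstinence, and total abstinent days. These are to be "determined by using data ascertained daily with the emocha Mobile Health app (emocha) or REDCap surveys".

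On who supplies daily reports:

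- The Time and Events Table has the row "Daily vaping exposure y/n via REDCap (for those not randomized to EUC". It is marked from baseline to week 12 and has dashes at weeks 16, 20 and 24.
- The opening of Section V lists what participants assigned to varenicline or placebo receive, including behavioral sessions "and a digital platform to report vaping behavior, study medication adherence, and tolerability". For EUC it lists advice to quit and non-directive support.
- The emocha paragraph in Section V.f says "Participants will record daily vaping either via emocha or REDCap", with no arm named.
- Study Compensation pays for "emocha medication adherence and REDCap survey completions (for those not randomized to EUC".

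On the Timeline Followback:

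- The table schedules it at every visit from enrollment to week 24, with no arm restriction. A footnote says that a modified version covering the past 7 days is used at the weekly visits.
- Section V.a describes "weekly visits which will include assessments (all participants", and Section V.d says "For participants randomized to the EUC arm, weekly sessions will only consist of non-directive support and assessments noted in the Time and Events Table".
- Section V.f says "A modified TLFB of vaping in the past 7 days will be administered at weekly intervention visits".

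Section VI gives methods for Hypotheses 1.1 to 1.6, 2.1 and 2.2. It does not mention Hypothesis 1.7.

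**The concern.** The hypothesis names one data source for comparisons with two control groups, and the schedule excludes one of those groups from that source. The contrasts with EUC cannot be run as stated.

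The analyst would then have to choose a substitute for EUC, possibly with the data in hand. One possible choice is to keep daily reports for varenicline and use visit-based recall for EUC. Nothing in the plan proposes this, but nothing rules it out. It would confound arm with method of measurement, and the timing of a first lapse or a count of abstinent days could differ between arms for that reason alone.

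**Working it through.** This is mainly a comparison of passages; the plan states no figure to reproduce.

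**1. Contrasts affected.** 5 endpoints × 2 comparators = 10 contrasts. Of these, 5 × 1 = 5 are against EUC.

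**2. Is daily reporting collected in EUC?** The table row excludes EUC in terms. The opening of Section V agrees, since the platform appears only in the list for the two pill arms. The emocha sentence in Section V.f names no arm, but it directly follows a sentence about medication reminders that is limited to varenicline or placebo. A general sentence in that position does not override an explicit exclusion in the schedule.

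**3. Corroboration from payment.**

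- Pill arms, visits: 30 + 4×30 + 50 + 3×30 + 50 + 3×30 + 50 + 3×30 = 570. Adding 168 for emocha and surveys gives 738, the printed total. At up to $2 a day, 168 / 2 = 84 days, which is 12 weeks × 7.
- EUC: 30 + 4×30 + 100 + 3×30 + 100 + 3×30 + 100 + 3×30 = 720, the printed total, with 0 for emocha and surveys.

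The totals are consistent with no daily reporting in EUC. They do not prove it, for the reason given under objection.

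**4. Is another source named?** No. Section VI goes from Hypotheses 1.1–1.6 to 2.1 and 2.2.

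**5. Can the Timeline Followback fill the gap?** Its row carries no arm restriction, weekly visits include assessments for all participants, and the EUC weekly sessions contain the table's assessments. The most it can cover, with every visit attended, is:

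- Weeks 1–3, 5–7 and 9–11: 9 visits × 7 days = 63 days.
- Weeks 4, 8 and 12: 3 visits × 7 days = 21 days, if the full version looks back at least 7 days.
- Together: 63 + 21 = 84 of the 84 treatment days.
- Weeks 16, 20 and 24: visits are 4 weeks apart, so a look-back of at least 4 × 7 = 28 days is needed to leave no gap.

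These counts assume that the instrument is recorded day by day. Neither its resolution nor the look-back of the full version is stated.

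**6. Varenicline versus placebo.** Both arms have daily reports, but only to week 12. The named source cannot show a relapse after week 12 in any arm.

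**The case against.** The best textual defence is the arm-neutral sentence in Section V.f, which could be read to include EUC. If that was the intention, the table and the payment text are what need correcting. The passages conflict on either reading, and the explicit exclusion is the stronger evidence.

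The payment evidence is weaker than it looks. The $168 covers recorded dosing as well as surveys, and EUC participants have no study medication to record. Payment also shows what is rewarded, not what is collected. This objection stands, so the case rests on the table and on Section V.

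The remedy could also be called a preference. Removing EUC from the hypothesis, collecting daily reports in EUC, or using the Timeline Followback for all contrasts would each resolve the conflict. That is fair. The essential requirement is the same source in both arms of any one contrast.

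It is also fair that the suitability of the Timeline Followback rests partly on properties that the plan does not state. In addition, Section V.f places the weekly version at intervention visits, which read literally might leave out EUC. The table footnote and the description of EUC weekly sessions point the other way.

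A reader might infer that EUC has no vaping data over time, or that the cessation results are in doubt. The documents support neither. The Timeline Followback is scheduled in EUC, and Hypotheses 1.1 to 1.6 rest on self-report at visits with cotinine verification, not on the daily reports.

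**Conclusion.** Wrong as written, and minor. The five EUC contrasts in Hypothesis 1.7 have no EUC data from the source that the hypothesis names, and no later section supplies another. The defect lies in the named source and is confined to one exploratory hypothesis.

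It would be too strong to say that the varenicline–placebo contrast is wholly unaffected. Its data source is available in both arms only through week 12.

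That the hypothesis and the schedule conflict follows from the text and needs no assumption. That the Timeline Followback can replace the daily reports depends on day-by-day recording, on a look-back that reaches the previous visit, and on visits being attended.

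**What to change.** - In Hypothesis 1.7, name the Timeline Followback (the weekly 7-day version plus the version used at monthly and follow-up visits) as the source in both arms of every contrast with EUC. State that daily reports in one arm will not be set against recall in the other.
- Keep daily reports, if wanted, for varenicline versus placebo through week 12 only. Use the Timeline Followback for any relapse endpoint that extends into follow-up.
- Confirm in the text that the Timeline Followback is recorded by day and that the full version reaches back at least to the previous visit.
- Align two sentences in Section V.f with the table: limit the daily-reporting sentence to the varenicline and placebo arms, and state that the weekly visits at which the 7-day version is given include the EUC sessions.

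**Cost.** No new data collection. Section VI has no method for Hypothesis 1.7 and the plan does not define lapse or relapse, so a short analysis paragraph is needed as well. Recall is coarser than daily reporting. Results against EUC and against placebo would rest on different sources and should not be compared directly, unless the Timeline Followback is used for all ten contrasts.
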